7.5.2 Primary Efficacy Endpoint

DFS will be compared between treatment arms using a two-sided log rank test, stratified by the three randomization stratification factors as recorded in IWRS.

The HR for DFS with its corresponding two-sided $100 \times (1 - \text{adjusted } \alpha)\%$ CI will be estimated via a stratified Cox model with treatment arm as the only covariate in the model. Adjustment on the CI will be based on the reallocated alpha level.

DFS for each treatment arm will be estimated and plotted using the KM product-limit method. Median survival time will be computed using the KM estimate and a 95% CI for the median will be computed based on a log-log transformation of the survivor function.

Source of DFS Event

The source of DFS event will be summarized by treatment group:

- Recurrence (local recurrence, regional recurrence, distant recurrence)
- Death

Status of Censored Subjects

The status of subjects who are censored in the DFS KM analysis will be tabulated for each randomized treatment group using the following categories:

- 1) Censored on randomization date
 - a) no baseline disease assessment
 - b) no on-study disease assessment and no death
 - c) no on-study disease assessment but death with prior subsequent therapy or second primary cancer
- 2) Censored on date of last evaluable disease assessment on-study
 - a) Received subsequent anti-cancer therapy
 - b) Second non-esophageal and non-GEJ primary cancer
 - c) Still on treatment
 - d) In follow-up
 - e) Off study
 - i) lost to follow-up
 - ii) subject withdrew consent
 - iii) other

DFS rates at fixed time points (e.g. 6 months, depending on the minimum follow-up) will be presented along with their associated 95% CIs. These estimates will be derived from the Kaplan-Meier estimate and corresponding CIs will be derived based on Greenwood formula for variance derivation and on log-log transformation applied on the survivor function.

7.5.2.1 Sensitivity Analyses

The following four sensitivity analyses are planned for DFS to evaluate the robustness of the primary analysis of DFS.

- *Stratified analysis using stratification factors as obtained from the baseline CRF pages (instead of IWRS).* This analysis will be performed only if the stratification factors at randomization (as per IWRS) and baseline are not concordant for at least 10% of all randomized subjects considering all three stratification factors together.
- *Analysis using a 2-sided, un-stratified log-rank test and an un-stratified Cox proportional hazards model with treatment as the single covariate*
- *Analysis for subjects with no relevant deviation and those receiving at least one dose of study drug (per protocol subjects).* This analysis will be conducted only if there are more than 10% subjects with relevant protocol deviations.

Each of the above analysis will use the same significance level as the corresponding primary analysis. Estimate of the HR, its two sided $100(1-\alpha)\%$ CI and p-value will be presented.

- A multivariate stratified (by factors as specified in [Section 2.2](#)) Cox model will be fitted to assess the treatment effect when adjusted for potential prognostic factors. The following potential prognostic factors will be included in the model. A backward selection approach, starting from the full model, will be used as primary method with a significance level set to 0.10 of each of the covariates.
 - Age categorization ($< 65, \geq 65$)
 - Gender (Male vs. Female)
 - Baseline ECOG PS (0 vs. 1)
 - Region (Asia vs. RoW [including US/Canada, Europe])
 - Disease at study entry (EC vs. GEJ)
 - Time from beginning of neoadjuvant CRT to complete resection (< 6 weeks vs. ≥ 6 weeks)
 - Time from complete resection to randomization (< 10 weeks vs. ≥ 10 weeks)

If there is more than 10% imbalance between two arms within the subgroup of baseline demographics and disease characteristics, the factor may also be considered in the adjusted multivariate model.

For the multivariate analysis, HR and 95% CI will be provided for treatment variable and all covariates. Descriptive p-values will be provided.

- The key analyses of the primary endpoint DFS are the log-rank test and the Cox proportional hazards regression model, which are most efficient under the proportional hazard assumption. However delayed effect of immunotherapy interventions has been observed in many studies. The proportional hazards assumption will be examined by fitting a Cox model including a time-dependent variable defined by treatment by time interaction.

If the two-sided Wald Chi-square p-value of the treatment by time interaction is less than 0.1 or a visual examination of the K-M plot of the DFS indicates a delayed separation of the curves, the following analyses will be conducted in order to report the treatment effect when taking into consideration of the delayed effect.

– DFS will be compared between treatment groups via a 2-sided max-combo test. The max-combo test statistic is the maximum of 4 different Fleming-Harrington family weighted log-rank test statistics. $Z_m = \max (FH (0, 0), FH (0,1), FH (1,0), F(1,1))$, where $FH(p,\gamma)$ are the test statistics from the Fleming-Harrington family of test statistics. $FH (0, 0)$ corresponds to the log-rank test, while $FH (0, 1)$ is more sensitive to late-difference alternatives, $FH(1,0)$ is more sensitive to early difference with decreasing treatment effect and $FH(1,1)$ uses weights at the median.

– The DFS hazard ratios will be estimated in 2 time periods. The periods will be defined by a cutoff point. The cutoff point will be calculated in two ways: 1) using a stratified time-dependent Cox model with effects for treatment and period-by-treatment interaction. The cutoff point will be estimated using a grid of possible cut off points and obtained by maximizing the partial log likelihood. Ties will be handled using the exact method. A two-sided 95% CI for the hazard ratio will also be presented. 2) use the pre-specified cutoff point for delay separation used in the sample size determination, ie.3 months.

Visual interpretation of the curves may lead to additional analyses post database lock with more cut off points.

Sensitivity analyses for DFS to investigate alternative censoring schemes

- *Analysis accounting for assessment on/after subsequent therapy:* DFS will be defined similarly to the primary definition except that events (recurrence or death) and disease assessments that occurred on or after subsequent anti-cancer therapy will be considered (no time point truncation). Although the statistical significance will be determined by the stratified log-rank test using the primary definition of DFS, This analysis will be used to support EMEA filing.
- *DFS accounting for two or more consecutively missing disease assessments prior to DFS event:* This analysis will be performed only if at least 10% of DFS events have two or more consecutively missing prior to disease assessments. In case a subject has two or more consecutively missing disease assessments, the subject will be censored at the last disease assessment date prior the DFS event.
- Analysis in which recurrence-free subjects who are lost to follow-up for any cause will be considered as having an event at the time of the last tumor assessment date prior to loss to follow-up.

Each of the above analysis will use the same significance level as the corresponding primary analysis. Estimate of the HR, its two sided $100(1-\alpha)\%$ CI and p-value will be presented.

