1.4.7.7 Rationale for the Stratification Factors

The stratification factors in this study are PD-L1 status (≥ 1% vs. < 1% or indeterminate or non-evaluable), pathological lymph node (positive ≥ ypN1 vs. negative ypN0) and histology (adenocarcinoma vs. squamous).

The rational of PD-L1 status as the stratification factor described in previous [Section 1.4.7.6](#).

AJCC stage II and III are the initial clinical diagnostic stages to determine eligibility however the subjects will be randomized after CRT and surgery in this study. Patient outcome might correlate with the initial diagnosis stage, but the best correlation with survival is associated with surgical pathology staging. Pathological lymph node positive status is reported to result in worse survival

in patients with gastroesophageal cancer after trimodality therapy.^{7,11} Thus, the pathological lymph status is a better stratification factor at randomization than the initial diagnostic AJCC stage. Squamous histology showed a higher pCR rate and survival compared to adenocarcinoma in the CROSS study.⁷ The HR of mOS for patients with squamous cell type was 0.48 (mOS 81.6 months vs. 21.1 months in CRT/surgery vs. surgery alone), however, the HR for patients with adenocarcinomas was 0.73 (mOS 43.2 months vs. 27.1 months in CRT/surgery vs. surgery alone). The higher pCR rate might contribute to improved survival in squamous histology compared to adenocarcinomas (49% vs. 23%). On the other hand, a meta-analysis of 12 randomized studies comparing neoadjuvant CRT versus surgery alone (n = 1854), shows the survival benefits for neoadjuvant CRT were similar in both subgroups: squamous-cell carcinoma (HR 0.80, 95% CI 0.68–0.93; p = 0.004) and adenocarcinoma (0.75, 95% CI 0.59–0.95; p = 0.02).⁷¹ Patients with non-pCR tumors (the target population for this study) were reported to have a worse survival compared to the population achieving a pCR tumors across both histologic subtypes.^{11,46} However, there are no reports to compare directly the survival or DFS between squamous and adenocarcinoma types in tumors with non-pCR. Therefore, the potential risk of unbalance in the two treatment arms by the different survival outcome of the two histology types might be mitigated by stratifying for histology.

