7.3.2 Demographics and Other Baseline Disease Characteristics

The following demographic and baseline disease characteristics will be summarized and listed by treatment group as randomized:

- Age (continuous)
- Age categorization (< 65, ≥ 65 and < 75, ≥ 75 and < 85, ≥ 85, ≥ 75, ≥ 65)
- Sex (Male vs. Female)
- Race (White, Black or African American, Asian, American Indian or Alaska Native, Native Hawaiian or Other Pacific Islander, Other)
- Region (US/Canada, Europe, Asia, Rest of the World [RoW])
- Baseline weight (descriptive statistics)
- Smoking status (current/former, never smoker, unknown)

- Baseline ECOG PS
- Disease at initial diagnosis (EC, GEJ cancer)
- Disease stage at initial diagnosis (Stage I, Stage II, Stage III, Stage IV)
- Disease at study entry (EC, GEJ cancer)
 - EC: body location (Lower third, middle third, upper third)
 - GEJ cancer: Siewert-Stein (Type I vs. Type II vs. Type III)
- Histology (adenocarcinoma, squamous cell carcinoma, other) (stratification factor: squamous vs. adenocarcinoma)
- Histological grade (G1, G2, G3, G4, GX)
- Pathologic TN classification at study entry
 - Tumor (ypT0, ypT1, ypT2, ypT3, ypT4, unknown)
 - Nodes (ypN0, ypN1, ypN2, ypN3, unknown) (stratification factor: ypN0 vs. ≥ ypN1)

- Time from complete resection to randomization (< 4 weeks, 4 - 10 weeks, < 10 - 16 weeks, > 16 weeks).
- Time from randomization to first dose date (≤ 3, 4 - 5, 6 - 7, 8 - 14, 15 - 21, > 21, Not Reported or Not Treated)

- HER-2 status at study entry (negative, positive, unknown)
- Microsatellite instability (MSI-H, MSI-L, MSI-S, unknown)
- EBV status (positive, negative, unknown)

- Baseline LDH (\leq ULN, $>$ ULN; $\leq 2*ULN$, $> 2*ULN$)
- Baseline hemoglobin ($<$ 10g/dL, \geq 10g/dL)

- Baseline PD-L1+ status based on a 1% cut off ($\geq 1\%$ vs. $< 1\%$ or indeterminate)
- Baseline PD-L1+ status based on a 5% cut off ($\geq 5\%$ vs. $< 5\%$ or indeterminate)
- Baseline PD-L1+ status based on a 10% cut off ($\geq 10\%$ vs. $< 10\%$ or indeterminate)

For the purposes of displaying baseline characteristics, stratification factors will be retrieved from the CRF.

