7.5.2.2 Consistency of Treatment Effect in Subsets

The influence of baseline demographic and disease characteristics on the treatment effect among all randomized subjects will be explored via exploratory subset analyses. The median DFS based on KM product-limit method along with two-sided 95% CIs will be produced for the following subgroups.

A forest plot of the DFS hazard ratios (along with the 95% CIs) will be produced for each level of the subgroups examined. The analysis comparing treatment (i.e., Hazard Ratio) will be conducted if the number of subjects in the subgroup category is more than 10.

- Age category (< 65, ≥ 65 and < 75, ≥ 75; < 65 and ≥ 65)
- Gender (male, female)
- Race (White, Black or African American, Asian, Other)
- Region (Asia, RoW [including US/Canada, Europe])
- ECOG PS (0 vs. 1)
- Disease at study entry (EC, GEJ cancer)
 - EC: (Lower third, middle third, upper third)
 - GEJ cancer: Siewert-Stein (Type I vs. Type II vs. Type II)
- Disease stage at initial diagnosis (Stage I-II, Stage III-IV)
- Histology (stratification factor; squamous vs adenocarcinoma)
- Histological grade (G1/G2, G3/G4, GX)
- Pathologic lymph node status (stratification factor; ypN0 vs. ≥ ypN1)
- Pathologic tumor status (ypT0, ypT1/ypT2, ypT3/ypT4, unknown)

- Time from beginning of neoadjuvant CRT to complete resection (< 6 weeks vs. ≥ 6 weeks)
- Time from complete resection to randomization (< 10 weeks vs. ≥ 10 weeks).

- HER-2 status at study entry (negative, positive, unknown)
- Microsatellite instability (MSI-H, MSI-L, MSS, unknown)
- EBV status (positive, negative, unknown)
- Baseline PD-L1+ status based on a 1% cut off (≥ 1% vs. < 1% or indeterminate)
- Baseline PD-L1+ status based on a 5% cut off (≥ 5% vs. < 5% or indeterminate)
- Baseline PD-L1+ status based on a 10% cut off (≥ 10% vs. < 10% or indeterminate)

For the purposes of the subset analyses, stratification factors will be retrieved from the CRF.

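### The supportive covariate-adjusted Cox model for DFS and OS does not list pathologic tumor status (ypT), which can enter only through a discretionary imbalance rule; listing it is a low-cost improvement

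*SAP*

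**What the plan says.** SAP 7.5.2.1 describes the model as "A multivariate stratified (by factors as specified in" Section 2.2, that is, by PD-L1 status, nodal status (ypN0 against ypN1 or higher) and histology. Its purpose is to estimate the treatment effect after adjustment. "The following potential prognostic factors will be included in the model": age, gender, ECOG status, region, EC against GEJ, time from CRT start to resection, and time from resection to randomization. "A backward selection approach, starting from the full model, will be used as primary method", with a 0.10 retention level. P-values from this model are descriptive.

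Other factors have a conditional route: "If there is more than 10% imbalance between two arms within the subgroup of baseline demographics and disease characteristics", then "the factor may also be considered in the adjusted multivariate model".

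SAP 7.5.3.2 applies the section 7.5.2.1 analyses to OS where applicable.

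ypT appears elsewhere in the plan. SAP 7.3.2 tabulates "Tumor (ypT0, ypT1, ypT2, ypT3, ypT4, unknown") at baseline. SAP 7.5.2.2 uses "Pathologic tumor status (ypT0, ypT1/ypT2, ypT3/ypT4, unknown") as a DFS subgroup, and SAP 7.5.3.3 reuses the subgroups for OS. Protocol 1.4.7.7 says that "the best correlation with survival is associated with surgical pathology staging".

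**The concern.** Surgical pathology stage has a tumor part and a nodal part, and Protocol 3.3.1 bases eligibility on residual disease in either. The adjusted model carries the nodal part only, as a two-level stratum. The SAP gives no reason for leaving out the tumor part. The SAP document history shows that version 3.0 added sensitivity analyses to 7.5.2.1 and added pathologic tumor status to the subgroups in 7.5.2.2. The covariate list does not include it, which is consistent with an oversight but does not prove one.

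What is at stake is how convincing one robustness analysis is. If ypT is prognostic, a modest chance imbalance stays in the adjusted HR. If ypT is brought in later through the imbalance clause, the choice is made after the arms have been compared and will look data-driven.

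**Working it through.** **Inputs from the documents.** 760 subjects at 2:1, so about 507 and 253; 440 DFS events at an average HR of 0.72; 460 OS events at an average HR of 0.73 (SAP 5.2, 5.3).

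**Inputs that are assumed.** The documents give neither the ypT distribution nor its prognostic effect. I take a two-way split (ypT3/4 against lower) with a ypT3/4 share of 30% to 60% and a prognostic HR of 1.5, 2.0 or 2.5.

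**1. The plan's own power.** Single-look Schoenfeld approximation, power = Φ(√(D × 2/9) × |ln HR| − 1.96):

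- DFS: √(440 × 2/9) × 0.3285 − 1.96 = 9.888 × 0.3285 − 1.96 = 1.288, giving 90.1% (SAP: about 91%).
- OS: √(460 × 2/9) × 0.3147 − 1.96 = 10.111 × 0.3147 − 1.96 = 1.222, giving 88.9% (SAP: about 90%).

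Both agree to within about 1 point. Nothing below changes them.

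**2. How often the imbalance clause would act.** I read the 10% as percentage points. SD of the difference = √(p(1 − p)(1/507 + 1/253)).

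- p = 0.30: SD 3.53 points, P(difference above 10 points) = 0.5%
- p = 0.40 or 0.60: SD 3.77 points, 0.8%
- p = 0.50: SD 3.85 points, 0.9%

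**3. Size of a chance imbalance.** At p = 0.55, SD = √(0.55 × 0.45 × (1/507 + 1/253)) = 0.0383, with a 95% range of ±1.96 × 0.0383 = ±7.5 points. The treatment HR is multiplied or divided by about (ypT HR)^imbalance:

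| Assumed ypT HR | One SD (3.8 points) | Edge of 95% range (7.5 points) | 9 points, just under the trigger |
|---|---|---|---|
| 1.5 | 1.6% | 3% | 4% |
| 2.0 | 2.7% | 5% | 6% |
| 2.5 | 3.6% | 7% | 9% |

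As an example, a 9-point excess of ypT3/4 on nivolumab with a ypT HR of 2.0 turns 0.72 into 0.72 × 1.064 = 0.77. The reverse imbalance gives 0.72 / 1.064 = 0.68.

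**4. Average effect of omission.** Two DFS simulations, both stopped at 440 events. Simulation A uses the piecewise hazards of SAP Table 5.1-1, 36-month uniform accrual, a node stratum (assumed 57% positive, HR 1.8), a 55% ypT3/4 share and 2,000 replicates. Simulation B uses exponential times with a true conditional HR of 0.72, no strata, a 50% or 60% share and 1,500 replicates. Mean treatment HR without and with ypT in the model:

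| Assumed ypT HR | A, 55% | B, 50% | B, 60% | Shift toward 1 |
|---|---|---|---|---|
| 1.5 | 0.723 / 0.719 | 0.7227 / 0.7187 | 0.7239 / 0.7200 | 0.004 |
| 2.0 | 0.732 / 0.722 | 0.7315 / 0.7208 | 0.7271 / 0.7164 | 0.010–0.011 |
| 2.5 | 0.734 / 0.718 | 0.7381 / 0.7185 | 0.7357 / 0.7191 | 0.016–0.020 |

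With a ypT HR of 1.0, simulation B shows no shift (0.7218 / 0.7216 and 0.7186 / 0.7184). The 95th percentile of the single-trial relative difference between the two HRs in B is about 4%, 7% and 9–10% for ypT HRs of 1.5, 2.0 and 2.5.

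OS was not simulated. Neither simulation models the link between ypT and nodal status.

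**The case against.** A reader might infer that the adjusted HR omits a main prognostic factor. The documents do not support that. Protocol 1.4.7.7 contrasts pathology staging with initial AJCC stage and then uses the contrast to justify nodal status, which is already a stratum of this model. It singles out node positivity, not ypT, as worsening survival. ypT is a plausible covariate because it is part of surgical pathology stage, and no more than that is shown.

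A reader might also infer that ypT is left unbalanced by design, or that adding it would gain power. Randomization balances ypT in expectation; it is only not stratified. The model has descriptive p-values and no significance level of its own, so no confirmatory power is at issue. The average shift in step 4 arises without systematic imbalance. It reflects non-collapsibility of the HR, not confounding.

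Further points on the other side are fair. The list does not claim to be complete, and histologic grade and initial stage are absent too. The baseline table and the ypT subgroup HRs would let readers see an imbalance. A typical one-SD imbalance moves the HR by under 4% even at the top of the assumed range.

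Timing also matters. The rationale for Revised Protocol 04 says the first planned interim was completed before OS event tracking began in 2021, and SAP 5.4 places the DFS interim analysis at that look. A DFS covariate added now may not be pre-specified relative to those data. The same rationale says the sponsor remains blinded to OS events by arm.

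What survives is narrow: ypT is not listed, and the only route in is discretionary and would seldom open.

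**Conclusion.** The point holds as a modest improvement to a supportive analysis. SAP 7.5.2.1 adjusts for the nodal part of surgical pathology stage and not, by default, for the tumor part. Under an assumed ypT HR of 1.5 to 2.5, omission moves the adjusted HR by about 0.004 to 0.02 toward 1 on average, and a chance imbalance at the edge of its 95% range moves it by about 3% to 7% either way. Every size here rests on an assumed ypT share and effect; if ypT carries little prognostic weight beyond nodal status, the gain is close to nil. The primary stratified log-rank test, its HR, the alpha allocation and the stated power are untouched.

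**What to change.** In SAP 7.5.2.1, add pathologic tumor status at study entry to the fixed covariate list, in the four levels already defined in SAP 7.5.2.2 with unknown as its own level. State that backward selection keeps or drops it as a whole. Say in SAP 7.5.3.2 that the same list applies to OS. If DFS has already been unblinded, label the DFS model with ypT as supplementary and report it beside the model with the current list. Leave the primary analyses as they are.

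The cost is a short SAP edit and a variable already on the database. Four levels use at most three degrees of freedom, against about 440 DFS or 460 OS events. Eligibility requires at least ypN1 or ypT1, so eligible ypT0 subjects are node-positive; that level will be informed only within the node-positive strata and may be small.

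### The covariate-adjusted Cox sensitivity model is picked by backward selection and an optional imbalance clause, so the 95% CIs promised for its covariates are not valid and the model is not fixed in advance

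*SAP*

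**What the plan says.** SAP 7.5.2.1 lists analyses "planned for DFS to evaluate the robustness of the primary analysis of DFS". The fourth is a multivariate Cox model stratified by the randomization factors. It opens with "The following potential prognostic factors will be included in the model" and names seven two-level factors: age, gender, ECOG PS, region, EC versus GEJ, time from start of neoadjuvant CRT to resection (split at 6 weeks), and time from resection to randomization (split at 10 weeks).

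Two rules then let the data change that list:

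- Selection: "A backward selection approach, starting from the full model, will be used as primary method with a significance level set to 0.10".
- Imbalance: "If there is more than 10% imbalance between two arms within the subgroup of baseline demographics and disease characteristics", then "the factor may also be considered in the adjusted multivariate model".

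The section promises an HR and 95% CI for treatment and for all covariates, and on testing says only "Descriptive p-values will be provided". SAP 7.5.3.2 applies the same sensitivity analyses to OS where they fit.

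The primary analysis in SAP 7.5.2 involves no selection: "DFS will be compared between treatment arms using a two-sided log rank test, stratified by the three randomization stratification factors as recorded in IWRS", with the HR from a stratified Cox model containing treatment alone.

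**The concern.** An analysis meant to test robustness should be settled before the data are seen. Here the section does not agree with itself. The seven factors are to be in the model and reported with intervals, yet selection can remove any of them. Treatment is not said to be forced in. Calling backward selection the primary method implies another method, and none is named.

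The imbalance clause does not say whether 10% is absolute or relative, which of the many baseline characteristics in SAP 7.3.2 qualify, how multi-level factors are judged, or who decides. Two careful programmers could therefore report different adjusted models from the same data.

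Intervals computed after selection, as if the model had been fixed, also do not have their stated coverage for the covariates that survive.

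**Working it through.** **1. The event counts.** SAP 5.3 gives 760 subjects at 2:1, 440 DFS events, HR 0.72, two-sided 0.05 and about 91% power. With the Schoenfeld formula, power = Φ(√(440 × 2/9) × |ln 0.72| − 1.96) = Φ(9.888 × 0.3285 − 1.96) = Φ(1.288) = 0.901. With the planned interim look it is 0.895 under proportional hazards. For OS, 460 events and HR 0.73 give 0.889 against about 90%. The SAP used piecewise hazards, which could explain the small gaps, so the event counts can be relied on.

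**2. Is selection needed?** Seven binary factors plus treatment make 8 parameters. Stratification uses none.

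| Analysis (SAP Table 5.1-3) | Events | Events / 8 |
|---|---|---|
| DFS interim | 374 | 46.8 |
| DFS final | 440 | 55.0 |
| OS interim 1 | 299 | 37.4 |
| OS interim 2 | 368 | 46.0 |
| OS final | 460 | 57.5 |

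Against an assumed strict benchmark of 20 events per parameter, even 299 events support 14 parameters.

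**3. Effect on treatment.** Simulation with 760 subjects and 440 events, assumed factor prevalences of 15 to 40%, and treatment forced in:

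- Null rejection at 0.05 (5,000 runs) was 4.7% for both models with no prognostic factor. It was 5.1% (full) and 5.3% (backward) with every factor at HR 1.25.
- At a true HR of 0.72 (700 runs) the mean adjusted HR was 0.713 for both.
- The mean absolute difference in log HR was 0.006 to 0.007, with a maximum of about 0.05.

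**4. Effect on the covariate intervals.** Take one factor with z = estimate/SE and δ = true log HR/SE. It is kept if |z| > 1.645. Its 95% CI covers the truth if |z − δ| < 1.96.

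- δ = 0: kept with probability 0.10. The CI misses with probability 0.05, and every miss is among those kept. Coverage given retention = 1 − 0.05/0.10 = 0.50.
- δ = 1: kept with probability 0.2595 + 0.0041 = 0.2636. Kept and missed = 0.025 + 0.0041 = 0.0291. Coverage = 1 − 0.0291/0.2636 = 0.89.
- δ = 2: kept with probability about 0.639. Kept and missed = 0.025. Coverage = 1 − 0.025/0.639 = 0.96.

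Simulation agrees. Retained null factors were covered 46 to 52% of the time. Coverage over all retained factors was about 90% with four factors at HR 1.25 and three null, and about 95% with all seven at 1.25. The failure is therefore confined to null and weak factors.

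Such factors will often be kept. If none of the seven were prognostic, at least one survives with probability 1 − 0.9⁷ = 0.52, assuming independence.

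**5. How often the imbalance clause is triggered.** For a binary factor at 50% prevalence, reading 10% as percentage points, SE = √(0.25 × (1/507 + 1/253)) = 0.0385, so P(|difference| > 0.10) = 0.009. For any of ten such independent factors it is 1 − (1 − 0.0093)¹⁰ = 0.09. At 20% prevalence it is 0.001 for one factor.

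**The case against.** The best defence is that nothing is decided on this model. Its p-values are descriptive, the primary test involves no selection, and the type I error scheme in SAP 7.5.1 is not touched. Robustness is also examined by other sensitivity analyses, including alternative censoring schemes. This stands, and it keeps the point minor.

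A reader might infer that the treatment HR is reported with understated uncertainty. The documents give no ground for that and step 3 speaks against it: under randomization the covariates are unrelated to treatment except by chance, so dropping some changes little.

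A reader might also count 2⁷ = 128 possible models and see analyst freedom. That does not follow. The candidates, cut-points, direction and 0.10 level are stated, so for a given dataset backward selection leaves little choice. The real freedom lies in the imbalance clause. That clause looks at baseline data rather than outcomes and would seldom be triggered.

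Two practical objections stand and shape the fix:

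- Events per parameter says nothing about sparse levels. SAP 5.1 puts the median time from start of CRT to completed surgery at about 6 months in its reference trial, so the level below 6 weeks may be nearly empty.
- The protocol's rationale for Revised Protocol 04 says the first planned interim was complete before blinded OS tracking began in 2021. SAP 5.4 places the DFS interim in that look. A changed DFS model can no longer be presented as pre-specified.

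**Conclusion.** The concern holds in a limited form. The section contradicts itself on whether the seven factors are in the model, leaves additions to discretion after baseline data are seen, and reports 95% CIs for retained covariates that are not valid after selection: 50% coverage for a null factor and 89% for a weak one (δ = 1). Event numbers give no reason to select.

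It would be wrong to conclude that the primary DFS result, the error control or the adjusted treatment HR is compromised. The treatment HR moved by less than 1% on average in simulation (e^0.007 = 1.007).

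The treatment result rests on assumed prevalences and covariate effects, with treatment forced in and the imbalance clause not modelled. The 50% figure needs only approximate normality of the estimate. The gain from a change is in pre-specification, reproducibility and honest covariate intervals.

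**What to change.** Amend SAP 7.5.2.1, and 7.5.3.2 by reference, as follows:

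- Fit treatment plus the seven listed factors, stratified as in the primary analysis, with no selection and treatment always retained. Report HRs and 95% CIs from that one model.
- Set a rule, applied to pooled blinded counts, for recoding or omitting a factor with a sparse level. Name CRT start to resection below 6 weeks as the likely case. SAP 7.5.2.2 already requires more than 10 subjects in a category for a subgroup HR; a similar minimum on pooled events would serve.
- Delete the imbalance clause, or state that any model using it is post hoc.
- Apply this prospectively to any OS analysis not yet unblinded. For DFS, report the full model as supplementary beside the one already specified.

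The cost is a few lines of SAP text and less programming for the model itself. The downside is that one covariate HR may be imprecise.
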